Diagnostic testing for SARS-CoV-2 is intended to identify occurrence at the individual level and is performed when there is a reason to suspect that an individual may be infected, such as having symptoms or suspected recent exposure, or to determine resolution of infection. Examples of diagnostic testing include testing symptomatic individuals who present to their healthcare provider, testing individuals through contact tracing efforts, testing individuals who indicate that they were exposed to someone with a confirmed or suspected case of coronavirus disease 2019 (COVID-19), and testing individuals present at an event where an attendee was later confirmed to have COVID-19. The U.S. Food and Drug Administration’s (FDA) [FAQs on Testing for SARS-CoV-2](#) also address diagnostic testing for SARSCoV-2. Screening tests for SARS-CoV-2, on the other hand, are intended to identify occurrence at the individual level even if there is no reason to suspect infection—e.g., there is no known exposure. This includes, but is not limited to, screening of non-symptomatic individuals without known exposure with the intent of making decisions based on the test results. Screening tests are intended to identify infected individuals without, or prior to development of, symptoms who may be contagious so that measures can be taken to prevent further transmission. Examples of screening include testing plans developed by a workplace to test its employees, and testing plans developed by a school to test its students, faculty, and staff. In both examples, the intent is to use the screening testing results to determine who may return and the protective measures that will be taken. FDA’s [FAQs on Testing for SARSCoV- 2](#) also address screening testing for SARS-CoV-2. In sum, a screening COVID-19 test is one that is specific for SARS-CoV2 but has a lower sensitivity (i.e. ability to pick up the virus) than that of a diagnostic test. Thus, even those who have a negative screening test should be considered potentially infectious and must adhere to social distancing and masking rules as per all the other passengers on the plane. Those who are tested positive on the screening test must be assumed to have COVID-19 until proven otherwise by a confirmatory RT-PCR test (which is the gold standard). This approach of using “point-of-care” screening tests was recently advocated by The New England Journal of Medicine.¹⁰

Primary Objective

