- Study Coordinator stationed here with YVR staff (all wearing masks and are able to maintain appropriate distance)
- Study banners stationed here, with high-level details including steps and eligibility criteria (see “Banners”).
- Appropriate distancing markers on the floor to remind study participants to maintain distance while waiting in line
- Welcome Package: bottled water, pens, brochure (see “General Brochure”), and basic study plan (no informed consent form)
- Have alcohol-based hand rub (ABHR) station available to facilitate hand hygiene
- Provide a mask if passenger is not wearing mask
- Check basic inclusion/exclusion criteria
- Answer basic questions about the study
- Inform the risk of denied boarding, if screened positive
- If interested, direct to Informed Consent Area or Citizen Care Pod (5 stations) or wait inside terminal (5 seats allowing physical distancing with dividers)

Citizen Care Pod

- Passenger (potential study subject) will sanitize hands upon entry
- Potential study subject will sit at 1/5 station, facing curb-side side (these 5 stations will have partitions between participants as a physical barrier)
- Clinical Coordinator (all wearing PPE – gown, mask, shield, and gloves, more details below) will come up behind the subject to go through the informed consent
- Once signed consent form, proceed to collect NP swab and oral rinse
- Make sure the subject has no signs of bleeding after NP swab, and rest
- The subject will be given a questionnaire and directed outside of the Care Pod
- Another hand sanitization station will be available for subjects as they exit

Rapid COVID-19 Testing On Site

- For Phase 1, only the NP swab sample will be tested on site using the rapid test device. If the sample is positive, “Positive Screen Test Results” Protocol will be followed (see below). The remaining NP swab sample and oral rinse sample will be transferred back to research laboratory for confirmatory RT-PCR testing.
- For Phase 2, both the NP swab sample and the oral rinse sample will be tested on site using two separate rapid test devices. If either sample is positive, “Positive Screen Test Results” Protocol will be followed (see below). The remaining samples will be transferred back to research laboratory for confirmatory RT-PCR testing.

Results Office

- Results Office – a private room inside the YVR terminal

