- Second waiting area will be available outside of Results Office (these 5 stations will have partitions between participants as a physical barrier)
- Subjects will be asked to fill out the questionnaire on paper, using the pens (to be taken home by study participants) received from Welcome Booth
- After 15-20 min, screening results will be available from Study Coordinator
- Questionnaire will be handed back to Study Coordinator (to obtain results)
- Copy of signed consent form given back to subjects
- For WestJet passengers, WestJet will provide subjects with a discount offer for future flights in appreciation of their participation (see “WestJet Promotional Card”). This will be advertised in advance for Phase 2.

Study Team Members – Daily Self-Assessment

- Prior to working on site every day, each Study Team Member will assess for COVID-19 symptoms using the BC COVID-19 Self-Assessment Tool (<https://bc.thrive.health/covid19/en>)
- The Clinical Team Manager will also review WorkSafe BC policies regularly (<https://www.worksafebc.com/en/about-us/covid-19-updates/covid-19-returning-safe-operation>) for updates

Angry Passengers

- The Study Team will be following specific YVR/airline protocol when passengers become upset or irate.
- We will have a daily YVR/airline point of contact person on site to assist the Study Team at all times.
- When a passenger/subject should become upset or irate, our Study Team will inform our YVR/airline point of contact.
- At this point, the YVR/airline staff will work with security and necessary authorities to resolve the situation.

Unclaimed Results

- If a Study Coordinator advises airline staff results have not been collected by the passenger, airline staff can change the status of the passenger's boarding pass/booking so they will be unable to board the flight.
- Terminal pages can be made for the passenger asking them to return to the check-in area.

“Positive Screen Test Results” Protocol

- All subjects who screen positive will be provided with a face mask if they are not wearing one (they do not need a new mask if they already are wearing one)
- Study Coordinator informs subject that they have a “positive” result and contact airline to advise as well.
- Study Coordinator will inform subject on next steps including Study Team + airline contacts
- A new NP swab sample for confirmatory RT-PCR test will be taken by the trained research staff.

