- Passenger will be asked to self-isolate and monitor symptoms as per Public Health Guidelines
- Passenger will be provided a brochure with information and resources while waiting for confirmatory test results. The brochure includes public health information, details on rebooking, and frequently asked questions (see “Awaiting Confirmatory Test Results Brochure”).
- Study Coordinator hands over passenger to airline
- Airline agent returns any checked baggage to the passenger and informs on rebooking options
- YVR/airline will coordinate the transportation of the passenger to get home (either private car pickup – curbside level 3 or taxi – YVR will provide voucher)
- Upon receiving the result of the confirmatory test, the passenger will be contacted by clinical team manager
- Airline will be contacted by clinical team manager to be notified of the test result. The passenger travel profile will be updated accordingly

Provision of Test Report for Negative Test Result

- In the event of a negative test result, the Study Coordinator will, upon the subject's request, provide the subject with a printed test report in the format agreed between the parties which will include the following information:
 - Given name and surname of subject;
 - Type of test used;
 - Test result;
 - Date and time of test; and
 - Name and contact information for institute/laboratory that conducted the test.

Personal Protective Equipment

Study coordinators will have the following Personal Protective Equipment or PPE at their disposal for the purposes of the study:

- Surgical Gloves
- ASTM Level 3 Masks
- Face Shield
- Protective Gowns

Coordinators will dispose of PPE as per hospital protocol and re-apply new PPE once they have fully disinfected their work area and their person.

- new PPE does not need to be changed between study participants
- staff can change gowns when contaminated but gloves need to be changed between each study participant.

1. Read protocol: http://www.bccdc.ca/Health-Professionals-Site/Documents/COVID19_MOH_BCCDC_Donning.pdf
2. Hand hygiene: Clean all surfaces of hands and wrists
3. Don gown (cover torso and wrap around back, fasten in back of neck and waist), mask (secure ties at middle of head and neck, fit nose band to your nose and pull bottom down to completely cover chin), eye protection (place goggles or face shield over face and eyes and adjust to fit), and gloves (extend to cover wrist of gown)
4. Collect nasopharyngeal swab and oral rinse samples

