5. Doff gloves, hand hygiene
6. Replace gown and/or gloves if visibly soiled or contaminated
7. Repeat hand hygiene

Protocol for Cleaning Subject Testing Area

The consenting and testing area will be taking place inside the Citizen Care Pods which will be placed just outside of the departure terminal doors. Hand sanitizers will be available upon entry and exiting. All frequent touch surfaces (e.g., countertops, chairs, and door knobs) will be disinfected before the subject enters and after the subject exits.

Storage and Disposal of Biohazardous Materials and Samples

All Samples will be kept in a refrigerator located securely in the Citizen Care Pod. Disposable bins with biohazardous bags will also be inside the Citizen Care Pod. This fridge and disposable bins will be carefully monitored at all times. A curtain will be providing additional separation between passengers entering the Care Pod. Please see Care Pod schematic attached. At the end of each day our Study Team will securely transfer the samples in batches (securely tightened samples be packaged in batches into biohazard bags) to the research and clinical labs for validation and confirmatory testing, respectively. No samples will be left on site at the end of the day. Bins with disposables (inside the Care Pod) will be

cleared by YVR maintenance staff on a daily basis, with daily cleaning and disinfecting. Once the validation and clinical testing has been completed in research or clinical labs, the remaining samples will be disposed of or stored as per study protocol.

Data Collection

Subjects who enroll in the study are entered into the secure database. The following data will be collected using the Questionnaire:

- Age
- Sex
- Ethnicity
- PHN (optional)
- Date of enrolment
- Basic overall Medical history
- Lung Disease history
- Symptoms (e.g. fever, cough, shortness of breath, fatigue, pain, etc.)

Withdrawal from Study

Individuals will be withdrawn from the Study in case of any of the following reasons:

- Withdrawal of consent (no reason required)

Independent Ethics Committee or Research Ethics Board

Recruitment for this study will begin only after full approval of the protocol has been obtained from the Research Ethics Board.

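### Does calling two different RT-PCR tests confirmatory leave it unclear which result decides what happens to a passenger who screens positive?

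*Protocol*

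**What the plan says.** RT-PCR appears in four places in the protocol.

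- **Difference between diagnostic and screening tests.** A person with a positive screen is treated as infected unless a confirmatory RT-PCR, described as the gold standard, shows otherwise.
- **Rapid COVID-19 Testing On Site.** For Phase 1: "The remaining NP swab sample and oral rinse sample will be transferred back to research laboratory for confirmatory RT-PCR testing". For Phase 2: "The remaining samples will be transferred back to research laboratory for confirmatory RT-PCR testing".
- **Positive Screen Test Results protocol.** "A new NP swab sample for confirmatory RT-PCR test will be taken by the trained research staff". Further down the same list: "Upon receiving the result of the confirmatory test, the passenger will be contacted by clinical team manager", and "Airline will be contacted by clinical team manager to be notified of the test result". The travel profile is then updated.
- **Storage and Disposal of Biohazardous Materials and Samples.** Samples leave the airport each day and go "to the research and clinical labs for validation and confirmatory testing, respectively". A later sentence keeps two kinds of work apart: "Once the validation and clinical testing has been completed in research or clinical labs".

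**The concern.** The storage section and the on-site testing section give the research laboratory's work different names. One calls it validation and reserves confirmation for the clinical laboratory. The other calls it confirmatory, once for each phase, which makes a single typing error less likely.

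The word matters because it triggers action. The passenger and the airline are told the outcome of the confirmatory test, and the background section makes such a test the condition for no longer presuming infection. If research RT-PCR on leftover material carries the same name as RT-PCR on the new swab, a reader could ask which result the procedure means when the two differ. No sentence says outright which laboratory handles the new swab. The management algorithm is also the subject of Objective 1 and is assessed further in Phase 2, so one would want each of its steps to be identifiable from the text.

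**Working it through.** No sample size, error rate or other calculated figure is involved, so the check is a comparison of the passages.

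| Section | Specimen | Laboratory | Name given to the testing |
|---|---|---|---|
| Rapid COVID-19 Testing On Site, Phases 1 and 2 | leftover NP swab and oral rinse material | research | confirmatory RT-PCR |
| Positive Screen Test Results protocol | new NP swab | not named | confirmatory RT-PCR |
| Storage and Disposal, by order of listing | samples, not further specified | research | validation |
| Storage and Disposal, by order of listing | samples, not further specified | clinical | confirmatory, then clinical |

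**Step 1: is the conflict of labels real?** Yes. The first and third rows concern the same laboratory and use different words. For a passenger who screens positive, 2 leftover specimens + 1 new swab = 3 specimens are called confirmatory somewhere in the protocol.

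**Step 2: is the specimen behind the positive-screen action identified?** Yes. The bullets of the positive-screen procedure form one list under one heading. One specimen for confirmation is introduced there, the new swab. The next bullets deal with isolation and with a brochure for the time until the confirmatory result arrives. The list then refers to the result of the confirmatory test, with the definite article. Within that list the phrase has only one possible antecedent. The on-site section describes its own material as remaining, and the positive-screen list describes its swab as new, so the text separates the two.

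**Step 3: is the laboratory identified?** Only indirectly. The bullet on the new swab says who takes it, not who tests it. The storage section assigns confirmatory testing to the clinical laboratory, and its later sentence keeps clinical testing distinct from validation. The conflicting label in the on-site section concerns leftover material and does not mention the new swab.

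**Step 4: does anything done or analysed depend on which label is right?** Take each in turn.

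- *If the on-site section's label is kept:* leftover samples go to the research laboratory for RT-PCR, the new swab is tested by RT-PCR, and the positive-screen list acts on the new swab.
- *If the storage section's label is kept:* leftover samples still go to the research laboratory and RT-PCR is still the test named for them. The new swab is still tested by RT-PCR, and the list still acts on it.

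The two cases differ only in what the research laboratory's work is called. The Statistical Analysis paragraph names means, measures of spread and a positivity rate. None of these is defined there by the word confirmatory, so none of them changes.

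**The case for a change.** The best case for a change is that these are instructions about where samples go and who is told what. That is protocol content and cannot be left to a statistical analysis plan. On the plain text the research laboratory is given two roles, in three sentences across two sections. The on-site sentence follows directly after the instruction to start the positive-screen procedure, so it covers passengers who screen positive as well as those who screen negative. A new member of staff reading only the on-site section could take the research result for the confirmatory one. Correcting the wording would need no new sample or test.

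Part of this stands. The labels do conflict, and the laboratory for the new swab has to be inferred. It does not follow that the action step is undefined, because staff handling a positive screen work from the positive-screen list, and that list names its own specimen. Nor do the labels give opposite instructions. RT-PCR on leftover material can fairly be said both to confirm the antigen result and to validate the device. How leftover-sample and new-swab results would be compared, if they are, is a matter a statistical analysis plan may cover. That document is not at hand, so its absence here is not a fault. Counting every specimen that bears the label would show how widely the word is used, not how many results are affected.

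**Conclusion.** No change to the plan is called for. The protocol contains a clerical inconsistency, since the research laboratory's RT-PCR is confirmatory in one section and validation in another. It also leaves a small gap, since the laboratory that tests the new swab is not named where the swab is described. Neither alters which specimens are tested, which result is passed to the passenger and airline, or any summary named in the protocol.

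This rests on two readings. The first is that the positive-screen bullets are one continuous procedure, which their common heading supports. The second is that the clinical laboratory tests the new swab, which is inferred from the storage section. If the second were wrong, the specimen that the procedure relies on would still be the new swab, so the conclusion would hold. The documents give no basis for estimating how often leftover-sample and new-swab results would disagree, and the conclusion does not need such an estimate. Should the protocol be amended for other reasons, the two labels could be aligned then, but that would be tidying and would change no result.

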While the world waits for an effective and safe vaccine, according to experts in the field, the pandemic is likely to rage on for another 12 months or longer. For these sectors to survive (in the short-term), COVID-19 mitigation strategies are urgently needed. The current strategy that is used in many airports is to require airlines to conduct a health check of travellers before they board a flight and to check their body temperature at ticketing areas or boarding gates.

However, this strategy is not very effective because these measures are relatively insensitive (only a minority of COVID-19 patients have raised temperature at any given point in time during their disease course) and thus unlikely to identify individuals with SARS-CoV2, who are minimally symptomatic or completely asymptomatic at the time of travel. Indeed, public health experts have poignantly stated that transmission of the virus through asymptomatic individuals is the “Achilles’ Heel of Current Strategies to Control COVID-19”.⁴ This is because, unlike SARS-CoV1, the cause of the original SARS epidemic in 2003, SARS-CoV2 sheds at high concentrations from the nasal cavity even in asymptomatic individuals, who may harbor the virus but have yet to demonstrate any symptoms during the prodromal phase of the disease.⁵ Even with masking and social distancing, such individuals would be at a high risk of spreading the virus during air travel, especially during long flights.⁶ One approach to reducing the risk of SARS-CoV2 transmission during flights is to “screen” for those travelers who are likely to harbor the virus (even though they may have no or minimal symptoms) at airports across the country. However, the current diagnostic approach, which uses real-time reverse transcriptase polymerase chain reaction (RT-PCR) to detect the presence of viral RNA from nasopharyngeal swabs, cannot be easily deployed for this purpose

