The primary objective of this pilot study is to determine the feasibility and effectiveness of a COVID-19 screening program for passengers departing from YVR. This research study is conducted by The University of British Columbia (UBC) and Providence Health Care, sponsored by WestJet and Vancouver Airport Authority. The experimental study investigates point-of-care rapid test device for detecting SARS-CoV-2, the virus responsible for COVID-19. The study is investigating a method of rapid-testing for COVID-19 and will help inform the safest and most efficient way of testing departing passengers prior to security screening at Vancouver International Airport (YVR). This study is also evaluating a new passenger management system.

Summary of the Research Proposal

Purpose:

The purpose of this pilot study is to determine the feasibility and effectiveness of a COVID-19 screening program at YVR for WestJet and KLM passengers.

Hypothesis:

SARS-CoV-2 infection can be effectively screened using point-of-care rapid antigen assays.

Justification:

Passengers are required to wear masks and physically distance while traveling by air. However, the majority of general public is still worried about the potential risk of contracting COVID-19 on airplanes, especially during long flights. We need to develop methods and strategies to quickly screen for SARS-CoV-2 infection, prior to boarding flights.

Objectives:

1. To develop and deploy a management algorithm for COVID-19 screening at YVR that will involve the use of point-of-care rapid test device.
2. To evaluate the acceptability of such screening algorithm and determine the costs of deploying the program.

Research Design:

Study Population: Working in collaboration with WestJet and KLM we will invite all passengers meeting Inclusion/Exclusion on outbound flights from YVR Airport to participate in this study.

Phase 1: We will work with YVR and WestJet to enroll 200 subjects into the study. For this initial phase we are looking to determine the rate of positivity in the cohort. This initial phase is needed to evaluate the feasibility of this pilot program and to refine the initial management algorithm. Health Canada-approved Panbio Covid-19 Ag Rapid Test Device by Abbott Rapid Diagnostics (approved for Lab-based test and Point of care test on 2020-10-05) will be used in Phase 1.

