Phase 2: Strategies for achieving higher-throughput will be determined after completion of Phase 1. In phase 2, we will continue to work with YVR and WestJet, with the addition of KLM, to enroll 700 subjects into the study. Phase 2 will further assess the efficiency of our COVID-19 screening and passenger management algorithm.

The study is purposefully designed to be as minimally invasive to the passengers' travel plan as possible. The Study Plans for Phase 1 and Phase 2 are detailed below.

Statistical Analysis:

- When we aggregate the data for analysis, we will use basic statistics to determine mean, variance, standard deviation, and positivity rate...etc.

INVESTIGATIONAL PLAN

Phase 1 Recruitment

Inclusion Criteria:

1. The subject must be between 19 and 80 years of age.
2. The subject must be a resident of B.C.
3. The subject must have a ticket to board a WestJet flight departing from Vancouver International Airport (YVR).
4. Have a minimum of 75 minutes of free time prior to the scheduled flight's departure.

Exclusion Criteria:

1. We will exclude subjects who have previously tested positive for COVID-19 within the past 90 days
2. We will exclude subjects who cannot provide written informed consent

Phase 2 Recruitment

Inclusion Criteria:

1. Subject has access to accommodation in Canada for safe-isolation as per public health guidelines
2. Between the ages of 13 – 90
3. Travelling on any WestJet or KLM flight
4. Have a minimum of 70 minutes (if travelling within Canada) or 90 minutes (if travelling International) of free time prior to the schedule flight's departure

Exclusion Criteria:

1. We will exclude subjects who have previously tested positive for COVID-19 within the past 90 days
2. We will exclude subjects who cannot provide written informed consent or assent

Onsite Recruitment

For Phase 1, we will approach eligible passengers arriving at YVR terminal between 8 AM and 12 PM noon. For Phase 2, we will approach eligible passengers arriving at YVR terminal between 6:30 AM and 10:30 AM to capture WestJet's largest carrier departing at 9 AM, and between 11:30 AM and 3:30 PM on Thursday and Sunday for KLM flights. We will also mention a discount coupon will be given to WestJet passengers who successfully complete the study.

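### Does leaving known exposure off the data list spoil the positivity rate that the study sets out to report?

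*Protocol*

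**What the plan says.** Under Research Design, the protocol invites every passenger who meets the criteria. It says of Phase 1 (200 subjects): "For this initial phase we are looking to determine the rate of positivity in the cohort". Phase 2 (700 subjects) is to assess further how efficient the screening and passenger management are. The Statistical Analysis paragraph is purely descriptive: "we will use basic statistics to determine mean, variance, standard deviation, and positivity rate". The listed objectives are a screening algorithm, its acceptability and its cost.

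In both phases the only infection-related exclusion is "We will exclude subjects who have previously tested positive for COVID-19 within the past 90 days". Neither symptoms nor exposure bars a passenger.

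The Data Collection section lists age, sex, ethnicity, an optional health number, date of enrolment, basic medical history, lung disease history and "Symptoms (e.g. fever, cough, shortness of breath, fatigue, pain, etc". Exposure is not named. The questionnaire form is not part of the document.

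On timing, the Citizen Care Pod section says, after sampling: "The subject will be given a questionnaire and directed outside of the Care Pod". The Results Office section adds: "Questionnaire will be handed back to Study Coordinator (to obtain results".

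**The concern.** The section on the difference between diagnostic and screening tests describes diagnostic testing as "performed when there is a reason to suspect that an individual may be infected, such as having symptoms or suspected recent exposure". It therefore names two grounds for suspicion, and the data list records only one of them. A reader may conclude that the group with neither ground cannot be isolated.

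If a few passengers with known contact supplied many of the positives, the overall rate could be taken for the yield among ordinary travellers. A later analysis plan can use only what was collected, and asking about exposure after the result is known invites biased recall. That would make the gap hard to repair.

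**Working it through.** **1. What is promised.** The quantity named is the positivity rate in the cohort. Its numerator and denominator are both observed whether or not exposure is recorded. The document promises no split by exposure and no estimate for travellers without any ground for suspicion.

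**2. What the rationale compares with.** The introduction looks for "those travelers who are likely to harbor the virus (even though they may have no or minimal symptoms". The existing measures it calls insensitive are a health check and a body temperature reading. It does not mention exposure as something those measures pick up. To judge what the rapid test adds to them, one must separate travellers with symptoms from those with none or few. That split can be made from the listed data.

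**3. What the protocol means by screening.** The same section that defines diagnostic testing says that screening applies even where nothing suggests infection, and gives people without symptoms or known exposure as a non-exhaustive example. That wording widens the population. It does not confine screening to unexposed travellers.

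**4. The size.** The documents give no prevalence, share exposed or relative risk, so there is no figure to reproduce. All inputs below are assumptions except N = 200 + 700 = 900.

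Let s be the share with symptoms *or* exposure, p1 their positivity and p0 the positivity of the rest. The overall rate is s·p1 + (1 − s)·p0.

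| Case | s | p1 | p0 | Overall rate | Ratio to p0 | Expected positives (group with symptoms or exposure + rest) |
|---|---|---|---|---|---|---|
| Small | 0.02 | 0.03 | 0.010 | 0.0006 + 0.0098 = 1.04% | 1.04 | 0.54 + 8.82 = 9.36 |
| Large | 0.05 | 0.10 | 0.002 | 0.0050 + 0.0019 = 0.69% | 3.45 | 4.50 + 1.71 = 6.21 (4.50/6.21 = 72%) |

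These figures pool the recorded ground (symptoms) with the unrecorded one (exposure). In the large case the group holds 0.05 × 900 = 45 people. The two extremes show what the missing item costs:

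- *All 45 have symptoms.* The listed data separate them completely. The rate in the rest is 1.71/855 = 0.20%, and it is obtainable. Nothing is lost.
- *All 45 are exposed but free of symptoms.* The rate among symptom-free travellers is 6.21/900 = 0.69%. Symptom and temperature checks would have missed these people, so 0.69% is the right answer to the question in the rationale.

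In neither extreme does the missing item bias that comparison. Mixtures lie between the two, and the same reasoning applies.

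**5. Exposure alone.** Let f be the share exposed and RR their relative positivity. The overall rate divided by the rate in the unexposed is 1 − f + f·RR.

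- f = 2%, RR = 5: 0.98 + 0.10 = 1.08. Exposed share of positives: 0.10/1.08 = 9%.
- f = 10%, RR = 10: 0.90 + 1.00 = 1.90. Exposed share of positives: 1.00/1.90 = 53%.
- RR = 1: ratio 1.00 for any f.

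This measures how far the cohort rate differs from the rate in unexposed travellers, a second quantity that the protocol does not set out to estimate.

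**6. Precision of a split.** Illustrative counts near the large case, with exact 95% intervals:

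- all participants, 6/900 = 0.67% (0.25% to 1.45%)
- neither symptoms nor exposure, 2/855 = 0.23% (0.03% to 0.84%)
- symptoms or exposure, 4/45 = 8.9% (2.5% to 21.2%)

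The second interval spans a factor of about 0.842/0.028 = 30. Such a table could only be descriptive.

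**The case for a change.** The best argument for the concern is that a missing data item cannot be left to the analysis plan. The moment before the result is known is the clean time to ask, one extra question on an existing form is cheap, and the protocol itself names exposure as a ground for suspicion.

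Part of this stands. Exposure is not on the list, and anyone who wanted the subgroup with neither ground would have to collect it on the day.

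The rest is weaker. The questionnaire is not shown and the list uses broad headings, so it is not certain that the question is absent. Nor is the questionnaire the only contact before the result: staff check eligibility at the Welcome Booth, and a coordinator goes through consent. Answers would also be imperfect. Passengers are told at the Welcome Booth that a positive screen may cost them their flight, which gives them a reason to under-report contact. Above all, the argument shows that a further analysis would be interesting. It does not show that a planned one would be wrong.

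**Conclusion.** The concern does not hold. The protocol promises a cohort positivity rate with feasibility, acceptability and cost, and the missing item impairs none of these. The comparison behind the rationale turns on symptoms, which are recorded.

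The pooled ratios of 1.04 to 3.45 rest on assumed inputs and cannot be attributed to the missing item. The exposure-only ratios of 1.08 to 1.90 are also assumed, and they concern a quantity that the protocol does not undertake to report.

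The conclusion assumes that the existing health check does not ask about contact. The protocol does not describe its content and speaks of exposure only when it contrasts diagnostic with screening tests. If the check did ask, an exposure split would bear more on the added yield, but the planned cohort rate would still be sound.
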